4.2 Exclusion Criteria

1. Women who are pregnant or who are breast-feeding
2. Patients who have already started treatment of PCT with phlebotomy or low dose hydroxychloroquine or chloroquine, or who have been in such treatment in the past 30 days
3. Patients who have already started another treatment regimen for CHC, or who have taken such treatment in the past 30 days
4. HIV infection with CD4 counts at baseline less than 350/ μ L or with evidence of any active AIDS-defining illnesses
5. Ongoing active alcohol abuse, defined as a history of drinking more than 25 drinks of alcohol per week during most weeks in the prior 4 months (History of prior, but not current alcohol abuse will NOT be grounds for exclusion because we seek to treat subjects with PCT and CHC of the type typically seen in clinical practice)
6. Any ongoing active IV drug use
7. Patients who are taking Amiodarone or who have taken Amiodarone within 60 days prior to enrollment
8. Patients who are taking, or within the prior 28 days have taken, rifampicin or St John's wort (*Hypericum perforatum*), both of which are P-gp inducers, which may significantly reduce the drug levels and therapeutic effects of Harvoni
9. Uncontrolled diabetes (Hgb A1c $>9.5\%$ within 60 days prior to enrollment)
10. Chronic hepatitis B
11. Autoimmune hepatic liver injury—autoimmune hepatitis, primary biliary cholangitis/sclerosing cholangitis or overlap syndrome
12. Alcoholic hepatitis

13. Other metabolic disorders of the liver, e.g. Alpha 1 antitrypsin deficiency with ZZ Pi type, Wilson's disease
14. Prior known or suspected drug-induced liver injury within 6 months of enrollment
15. Known or suspected hepatocellular carcinoma
16. On liver transplant list, or current MELD >12
17. History of liver transplant
18. Estimated GFR (creatinine clearance) <30 mL/min (per Sofosbuvir being cleared by the kidney)
19. Serum ALT or AST >10x upper limit of normal
20. Serum bilirubin >2 mg/dL (excluding patients with known or suspected Gilbert's syndrome)
21. Any other comorbid condition, which in the opinion of the investigator precludes participation
22. Incarcerated individuals

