4.6 Study Procedures

Screening and Enrollment:

Potential subjects will be invited to take part and to sign informed consent forms. All participating centers will obtain CIRB approval.

Data collected at baseline will include demographic and clinical information. The screening laboratory tests will be:

- Serum HCV RNA by PCR (obtained within 30 days of enrollment)
- Anti-HCV antibodies
- CMP
- CBC with differential
- INR (if not done within 4 months of screening date)
- PTT
- Hepatitis B surface antigen
- Hemoglobin (Hgb) A1c
- Antibodies to HIV (if not done within 4 months of screening date). Those found positive will undergo HIV RNA and CD4 counts, to assure immune competence. Subjects with known HIV infection, with CD4 counts > 350/ μ L, whether receiving anti-HIV therapy or not, will **not** be excluded unless they require continuation of drug(s) contraindicated in subjects to receive Harvoni

- Spot plasma total porphyrins
- Spot urine delta-aminolevulinic acid (ALA), porphobilinogen (PBG), total porphyrins (including HPLC), and creatinine concentrations
- UROD enzyme activity and mutation analysis, if not previously done
- Serum iron and TIBC
- Serum Ferritin
- *HFE* genetic testing for C282Y and H63D, if not previously done
- Documentation of PCT symptoms and photographs of affected regions (hands, forearms, etc.)
- Alcohol and Tobacco use questionnaires
- Urine pregnancy for females of child-bearing potential

At baseline/screening, following informed consent, a standard interview to assess history of past and current alcohol use. HCV genotype should be confirmed prior to the screening visit as standard of care. History of smoking and current smoking status will also be assessed by interview and results recorded in suitable case report forms (CRFs). All prescription or over-the-counter drugs, including herbals, botanicals, and 'supplements' currently being taken or taken within the two weeks prior to screening, will be recorded, to include name, daily dose, and approximate duration of therapy (estimated to nearest month and year). Particular inquiry will be made regarding any and all estrogen use, including phyto-estrogens, as may be found in herbals and dietary supplements, such as black cohosh. All subjects will be evaluated by a hepatologist (the site PI or a Co-I) at baseline for liver disease based on the criteria detailed above for inclusion/exclusion.

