The therapy will be Harvoni at the usual dose (90 mg of ledipasvir and 400 mg of sofosbuvir) and duration for CHC therapy. One tablet taken daily for 8 weeks for patients without cirrhosis, not previously treated with HCV GT1 and HCV RNA < 6 million IU/mL; 12 or 24 weeks, duration to be determined based upon clinical features and prior treatment experience. 8 or 12 weeks for subjects with or without cirrhosis, not previously treated with anti-virals for CHC, and 24 weeks for subjects with cirrhosis who were previously treated with anti-virals for CHC without having achieved SVR. During the first year study visits will be monthly, and this includes the treatment period of either 12 or 24 weeks. To assess cure of HCV infection, repeated HCV RNA levels at 3, 6, and 12 months after end of Harvoni therapy will be done, as well as annually thereafter. Evaluation by a hepatologist at follow up visits will be as needed, determined by the screening lab test results and by clinical and lab findings at follow-up visits.

Lab measures to be checked monthly during therapy will include CBC, CMP, plasma total porphyrins, urinary total porphyrins (with HPLC), and levels of HCV RNA in serum by quantitative PCR (Section 4.7 Schedule of Events).

Porphyrin specific lab tests will be performed at the UTMB Porphyria Laboratory; all other labs will be performed at Covance Laboratories.

Subjects who have their treatment discontinued for any reason will continue to be followed until the end of the study, including longer-term follow up visits, unless they withdraw consent. If a subject becomes pregnant during the study Harvoni will be discontinued. The outcome of the pregnancy will not be followed as part of this study. Pregnancy during the study should be reported as an SAE.

Longer-Term Follow-up:

12 months after beginning treatment, subjects will be asked to return every four months for one year, with repeat of interval history and physical examination (especially to reassess the status of cutaneous lesions of PCT) and the above studies.

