4.7 Schedule of Events

	Screening (-30 to -1 Days)	Day 0	Day 30	Day 60	Day 90	Day 120	Day 150	Day 180	Day 210	Day 240	Day 270	Day 300	Day 330	Day 360	Day 480	Day 600	Day 720
			(Window +/- 7 days)														
			M1	M2	M3	M4	M5	M6	M7	M8	M9	M10	M11	M12	M16	M20	M24
Consent	X																
Complete Medical History	X																
Interval Medical History		X	X	X	X	X	X	X	X	X	X	X	X	X	X	X	X
Physical Examination	X	X			X			X			X			X	X	X	X
Skin Assessment (including pictures)	X	X	X	X	X	X	X	X	X	X	X	X	X	X	X	X	X
Alcohol & Tobacco use questionnaires	X																
Adverse Event/SAE Review														Each visit			
Urine Pregnancy	X																
Anti-HCV antibodies	X																
PTT	X																
Hepatitis B Surface Antigen	X																
HIV-1/HIV-2 Antibodies	X																
Serum Ferritin	X																
Serum iron and TIBC	X																
Complete Metabolic Panel\$	X	X	X	X	X	X	X	X	X	X	X	X	X	X	X	X	X
INR**	X																
HbA1c	X																
Erythrocyte UROD enzyme activity*	X																
UROD mutation analysis*	X																
HFE genetic testing*	X																
Hematology with Differential#	X	X	X	X	X	[X]*	[X]*	X	X	X	X	X	X	X	X	X	X
HCV RNA	X	X				[X]*	[X]*	[X]									
Plasma Total Porphyrins	X	X	X	X	X	X	X	X	X	X	X	X	X	X	X	X	X
Spot Urine ALA, PBG, Total Porphyrins	X	X	X	X	X	X	X	X	X	X	X	X	X	X	X	X	X
Fibroscan (if available at institution)	X														X		X
Dispense Study Drug [€]		X	X	X	X	X	X	X	X								

Hematology (complete blood count): white blood cell count (WBC), red blood cell count (RBC), hemoglobin, hematocrit, platelet count

\$Comprehensive metabolic panel: sodium, potassium, chloride, carbon dioxide, calcium, BUN, creatinine, glucose, and liver panel, including total protein, albumin, total bilirubin (TBR), alanine aminotransferase (ALT), aspartate aminotransferase (AST), alkaline phosphatase (AP)

*If not previously done

**INR (if not done within 4 months of screening)

[€]Drug is only to be dispensed at months 2-6 if additional therapy is warranted

[X]* Samples at these time points will be obtained only in subjects with cirrhosis who 24 weeks of Harvoni therapy is indicated; [X] Samples at these time points will be obtained 3, 6, and 12 months after the end of Harvoni treatment, and annually till end of study or EOT

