5.1 Study Oversight

The Study Chair has primary oversight responsibility of this clinical trial. The NIH appointed Data (Observational) Safety Monitoring Board (D/OSMB) has oversight responsibility of the Data Safety Monitoring Plan (DSMP) for this clinical trial. The D/OSMB will review accrual, patterns and frequencies of all adverse events, and protocol compliance every 6 months. The D/OSMB makes recommendations to the NIH regarding the continuation status of the protocol.

Each site's Principal Investigator and his/her research team (co-Investigators, research nurses, clinical trial coordinators, and data managers) are responsible for identifying adverse events. Aggregate reports- detailed by severity, attribution (expected or unexpected), and relationship to the study drug/study procedures – will be available from the DMCC for DSMB review. Adverse events will be reviewed at each study visit by the research team. A separate report detailing protocol compliance will also be available from the DMCC for DSMB review. The research team will then evaluate whether the protocol or informed consent document requires revision based on the reports.

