5.2 Definitions and Standards

The Rare Diseases Clinical Research Network defines an adverse event as: "...an unfavorable and unintended sign, symptom or disease associated with a participant's participation in a Rare Diseases Clinical Research Network study."

Serious adverse events include those events that "result in death; are life-threatening; require inpatient hospitalization or prolongation of existing hospitalization; create persistent or significant disability/incapacity, or a congenital anomaly/birth defects."

An unexpected adverse event is defined as any adverse experience, the specificity or severity of which is not consistent with the risks or information described in the protocol.

Expected adverse events are those that are identified in the research protocol as having been previously associated with or having the potential to arise as a consequence of participation in the study.

All reported adverse events will be classified using the current version of the Common Terminology Criteria for Adverse Events (CTCAE) developed and maintained by CTEP at the National Cancer Institute.

5.3 Expected/Known Risks/Discomforts/Adverse Events Associated with Study Intervention and Procedures: Definition of Expected Adverse Events

Drug Information for Harvoni

It was determined by the Food and Drug Administration that this study does not require an Investigational New Drug application.

Human Toxicity/ Adverse Events (adapted from package insert dated March 2015) The safety assessment of HARVONI was based on pooled data from three Phase 3 clinical trials of subjects with genotype 1 chronic hepatitis C (CHC) with compensated liver disease (with and without cirrhosis) including 215, 539, and 326 subjects who received HARVONI for 8, 12 and 24 weeks, respectively.

The proportion of subjects who permanently discontinued treatment due to adverse events was 0%, <1%, and 1% for subjects receiving HARVONI for 8, 12, and 24 weeks, respectively.

The most common adverse reactions ($\geq 10\%$) were fatigue and headache in subjects treated with 8, 12 or 24 weeks of HARVONI.

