5.5 RDCRN DMCC Adverse Event Monitoring Process

The DMCC will make adverse event reports available for review. Upon entry of a serious adverse event (SAE) into the DMCC database, the Study Chair, site PIs, the RDCRN D/OSMB medical review officer, and any additional agencies (if applicable-industry sponsor) will be notified immediately by email.

Serious adverse events: The NIH appointed Medical Review Officer (MRO) reviews the site investigator's report and determines causality (definitely not related, probably not related, possibly related, probably related, definitely related) of the adverse event. The MRO may request further information if necessary and possibly request changes to the protocol or consent form as a consequence of the adverse event. Any follow up reports or requested additional participant data will be entered into the DMCC Adverse Event Monitoring System by the reporting site and reviewed by the MRO. Completed AE reviews by the MRO will be sent to Study Chair, site PIs, and the appointed NIH officers.

If warranted, the MRO may request an ad hoc call with the DSMB to review the adverse event. All reported AE's will be reviewed during the regularly scheduled DSMB call. The DMCC Adverse Event Monitoring Process maintains audit trails and stores data (and data updated) and communication related to any adverse event in the study.

Non-serious expected adverse events: Except those listed above as immediately reportable, non-serious adverse events that are reported to or observed by the investigator or a member of his research team will be submitted to the system in a timely fashion (within 20 working days). The events will be presented in tabular form and given to the MRO and RDCRN D/OSMB on an annual basis. Local site investigators are also required to fulfill all reporting requirements of their local institutions.

The DMCC will post aggregate reports of all adverse events (serious/not serious and expected, unexpected) for the DSMB, site investigators and CIRB.

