5.7 Subject Discontinuation

An intent to treat approach will be used. All data acquired prior to termination for the reasons outlined below will be included in the primary analysis. Every effort will be made to conduct a final study visit with the participants and participants will be followed clinically until, if applicable, all adverse events resolve.

- Withdrawal of consent by the participant
- Withdrawal by the investigator if early stopping rules have been met: If there are Grade 4 toxicities, such as severe bradycardia with syncope, Harvoni will be stopped. Subject's PCT symptoms worsen significantly (as specified in section 5.3)
- Withdrawal by the investigator for other reasons
- Intercurrent illness or event that precludes further visits to the study site or ability to evaluate disease (e.g. mental status change, large pleural effusion).

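### The only scheduled pregnancy test is 1 to 30 days old at first dose, and the outcome of a pregnancy exposed to drug is not collected: a low-priority safety gap that is cheap to close

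*Combined protocol and SAP*

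**What the plan says.** All references are to the combined protocol and SAP.

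**Testing and eligibility**
- Criterion 1 of section 4.2 excludes "Women who are pregnant or who are breast-feeding".
- The screening laboratory list in section 4.6 includes "Urine pregnancy for females of child-bearing potential". In the section 4.7 schedule, the row "Urine Pregnancy" is marked in the screening column only (Day -30 to -1).
- The monthly on-treatment laboratory list in section 4.6 contains no pregnancy test.
- Day 0, when drug is first dispensed, has an interval history, a physical examination and a spot urine collection.
- Inclusion criterion 6 (section 4.1 and synopsis) ties the contraception requirement to the treatment period.

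**If pregnancy occurs**
- Section 4.6 stops Harvoni and adds: "The outcome of the pregnancy will not be followed as part of this study. Pregnancy during the study should be reported as an SAE".
- Section 4.6 keeps subjects who stop drug in follow-up to the end of the study, unless consent is withdrawn.
- Section 5.2 lists, among the results that make an event serious, those that "create persistent or significant disability/incapacity, or a congenital anomaly/birth defects".

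**Routes by which an outcome could still become known**
- Section 5.1: "Adverse events will be reviewed at each study visit by the research team".
- Section 5.4 sends any SAE to the manufacturer's drug safety department within 15 days.
- Section 5.5: "The MRO may request further information if necessary". It also has sites enter follow-up reports into the coordinating center's adverse event system.

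**The concern.** The plan treats pregnancy as a safety matter: it excludes pregnant women, stops drug on pregnancy and requires an SAE report. Two details fall short of that.

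First, a woman who conceives between the screening test and Day 0 can start Harvoni with no scheduled test that could show it. For those days the contraception criterion does not clearly apply either.

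Second, the report records that an exposure happened, but sites are told that how it ended lies outside the study. A birth defect, which section 5.2 classes as serious, would be learned of only if someone volunteered it or asked.

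What is at stake is the safety of a very small number of women and infants, and the completeness of the safety record.

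**Working it through.** The plan gives no figure for this point, so there is none to reproduce. The check has four steps.

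**1. Age of the test at first dose.** Inputs from section 4.7: screening on Day -30 to -1, first dispensing on Day 0. The test is 1 to 30 days old. A urine test also misses very recent conceptions; assume a detection lag of 10-14 days (not in the documents). The period in which a conception would go unseen is the age of the test plus the lag:
- Screened Day -1: 1 + 10 = 11 to 1 + 14 = 15 days.
- Screened Day -30: 30 + 10 = 40 to 30 + 14 = 44 days.
- With a Day 0 test: 0 + 10 = 10 to 0 + 14 = 14 days.

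The gain is 1 to 30 days whatever lag is assumed. The lag itself remains.

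**2. Can the outcome be collected within existing visits?** Inputs: treatment of 8, 12 or 24 weeks (section 4.8), that is 56, 84 or 168 days; visits monthly to Day 360, then Days 480, 600 and 720 (section 4.7). Assume 266 days from conception to delivery, or 280 if two weeks late.

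| Conception | Delivery at 266 days | Delivery at 280 days |
|---|---|---|
| Day 0 | 266 | 280 |
| End of 8 weeks | 56 + 266 = 322 | 336 |
| End of 12 weeks | 84 + 266 = 350 | 364 |
| End of 24 weeks | 168 + 266 = 434 | 448 |

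The latest delivery, Day 448, falls before the Day 480 visit and 720 - 448 = 272 days before the last one. A subject still attending needs no added visit; one who has left needs one contact.

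**3. How many pregnancies?** The number of women of child-bearing potential is not given. Assume 5-15% of the 49 subjects, which is 0.05 × 49 = 2.45 to 0.15 × 49 = 7.35 women, and contraceptive failure of 1-10% a year. Time at risk is the screening gap plus treatment: 1 + 56 = 57 days at the shortest, 30 + 168 = 198 at the longest. Expected pregnancies = women × yearly rate × days / 365:
- Low: 2.45 × 0.01 × 57/365 = 0.004.
- High: 7.35 × 0.10 × 198/365 = 0.40.

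A contraceptive-failure rate may be too low for the gap, where contraception is not clearly required. The high case can be stressed. Treatment alone contributes 7.35 × 0.10 × 168/365 = 0.34. The gap supplies 7.35 × 30/365 = 0.60 woman-years. For the total to reach one, the conception rate in the gap would have to be (1 - 0.34)/0.60 = 1.1 per woman-year, with every woman screened on Day -30.

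**4. Does any other section ask for the outcome?** The visit review (5.1) asks about adverse events in general. Section 5.4 carries the SAE report to the manufacturer. Section 5.5 lets the medical review officer ask for more and gives sites a place to enter it. None names the pregnancy or infant outcome, and the one sentence that does, in 4.6, says it will not be followed.

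**The case against.** **The plan already has a safety route.** Because section 4.6 makes pregnancy an SAE, each one reaches the study chair, the medical review officer and the manufacturer's drug safety department, and a channel for follow-up data exists. This stands, and it narrows the point. The 4.6 sentence limits what the study collects; the documents do not show whether the manufacturer pursues the outcome. It would be wrong to say that the outcome cannot become known. What remains is that no step plans to obtain it.

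**A reader might infer that 4.6 contradicts 5.7**, which says that "participants will be followed clinically until, if applicable, all adverse events resolve". The documents do not support that. The sentence is qualified, does not name pregnancy, and sits in a section on participants whose participation ends. A subject who stops drug for pregnancy stays in follow-up under 4.6, so 5.7 does not clearly cover her. Section 5.2 classifies a birth defect as serious but promises no active follow-up.

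**A reader might also infer a known fetal hazard.** None appears among the listed risks (sections 5.3 and 8.3). The drug is given at its usual dose, and FDA required no investigational new drug application. The point rests on the plan's own decision to exclude pregnancy and stop drug for it. The consent pages are not available, so any pregnancy wording there cannot be checked.

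**Few entrants may remain.** Activation was in August 2017 with a three-year enrolment target, so approval on 5 May 2020 falls about three months before the planned close. This weakens the case for the Day 0 test and the criterion 6 change, although the synopsis still lists the study as enrolling. It does not weaken the outcome sentence, which also covers subjects already enrolled.

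**Conclusion.** The point holds as a low-priority patient-safety improvement in two parts. The test on which the pregnancy exclusion relies is 1 to 30 days old at first dose, supplemented only by history and examination. The outcome of a pregnancy exposed to drug has no planned collection, although existing channels could carry it.

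Expected frequency is well under one pregnancy in the whole trial, about 0.004 to 0.40. That range rests on the assumed share of women able to conceive and the assumed failure rate, and may understate risk in the screening gap. The 1 to 30 days follow directly from the schedule. The claim that no extra visit is needed rests on the assumed 266-280 days to delivery and on continued attendance.

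The primary endpoint, power and decision rule are unaffected.

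**What to change.** 1. **Section 4.7:** add a urine pregnancy test at Day 0, before the first dose, for women of child-bearing potential, on the spot urine already collected.
2. **Criterion 6 (section 4.1 and synopsis):** require contraception from screening through end of treatment.
3. **Section 4.6:** replace the sentence declining follow-up with: *With consent, the pregnancy and infant outcome of any pregnancy conceived before or during Harvoni treatment will be collected as follow-up to the SAE report, at the next scheduled visit after delivery or by one contact.* Use the reporting channels in sections 5.4 and 5.5. Pregnancies conceived after treatment ends are outside this request.

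The cost is an amendment with central IRB review, consent wording for pregnancy and infant data, a few strip tests, and one question or contact per exposed pregnancy. Items 1 and 2 may reach few remaining entrants; item 3 keeps its value for those already enrolled.
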